### **Blinding**

The study will be double blinded to patients and investigators. The study team will include investigational pharmacists who will package the intervention RPS and placebo starch into packages labeled per FDA guidelines,

and will not share the labeling key code with any of the other study members who are performing the study. Labeling will also comply with labeling regulations under 21 CFR 312.6. As aforementioned in section 4.2 above, we will use stratified (by site) permuted block randomization and will generate randomization lists to be sent to the research staff members who will package the starch to deliver the designated packages to participants

### **Subject Recruitment and Retention**

Subjects will be identified via the use of an EHR compiled list of COVID-19 positive patients who are outpatients. We will use medical records to obtain phone numbers. We will contact patients via phone and before discussing any material pertaining to the study, we will first inform the patients that this call is regarding a research study and if they would like they can opt out, to ensure that the option of opting out is given to the patient as early as possible. If the patient agrees to hear information regarding the study, we will provide an oral presentation of the study. Additionally, we will also post flyers at testing centers to give participants information about the study and the option to opt out. After presenting the study to patients by phone, an informed consent document will be sent to the patient electronically for subjects to sign digitally. After informed consent is obtained, screening to ensure that participants meet the inclusion/ exclusion criteria will be performed via phone and EHR. All follow up will be via phone calls and EHR review. The above plan was put together in order to limit contact with COVID-19 positive patients as the alternative of approaching and following the patients in person will put the research staff and the community at large at risk as it will promote the spread of this highly infectious virus by bringing these patients to the health system.

### **Drug Information**

- This study investigates a food source that is being used as a drug but FDA offered a Discretionary Exemption to the IND application. While there are many potential sources for a potato-based or corn-based starch, we have chosen to use starch produced by Bob's Red Mill® because it is easily commercially available, economical and previously well tolerated in our preliminary data
- Some possible side effects to starch are flatulence (gas), abdominal bloating and chalky taste in the mouth. However, the majority of patients do not experience any symptoms when ingesting the dietary supplement. Below are the symptoms that may be experienced from the starch listed as possible, infrequent, and rare:

Possible 10-25 %: flatulence (gas), bloating, chalky taste in your mouth after drinking the starch, which resolves quickly

Infrequent 5-10 %: abdominal cramps, diarrhea, nausea, vomiting

Rare <5%: allergy to starch

Although very minimal adverse events and no serious adverse events were observed in our preliminary data, we have compiled a list of possible adverse events that will need to be reported to the safety monitoring coordinators.

- Contraindications

No contraindications to administration of this investigational agent other than the exclusion criteria noted. Specifically, should an enrolled subject develop one of the exclusion criteria (ie active Clostridium difficile infection or IBD) after enrollment and initiation of the study, they will be allowed to continue on study treatment. Meeting the primary end point of hospitalization is considered a contraindication to continue with the investigational agent.

The only concomitant medications prohibited on the study are anti-IL 6 inhibitors such as Tocilizumab, which is one of the exclusion criteria. This is usually a medication started as inpatient so we don't anticipate our patient population will be prescribed this drug after enrollment and while on investigational agent, since subjects will only continue to receive the investigational agent if they are not hospitalized.

- Interaction with other medications

As a dietary supplement and component of normal dietary intake, there are no anticipated interactions with other medications.

- Storage and stability: Store at room temperature, 59 °F to 86 °F. Avoid extremes of temperature. No need for refrigeration

- Preparation and Dispensing: Mix 2 tablespoons of dietary starch (~20 grams) with any amount water, juice, applesauce or any other cool substance to make palatable. Starch substance should not be heated or warmed

- Other administration instructions: No regulation for administration of starch with or without other food or medications. As this is a commercially available food product, subjects can keep any remaining product at the end

of study. We will determine compliance via questionnaire that will be utilized during phone follow ups. Doses should be administered twice daily. Although we suggest the doses be spread apart to minimize any potential GI disturbance, there is no limit as to how closely together doses can be given. For example, doses do NOT need to be given 12 hours apart and instead can be given at times that feel comfortable to the subject

- Missed doses should be documented by the research team during phone follow up
- Missed doses should simply be skipped with no need to make up this dose at a later time
- Availability: Commercially Available. Potato starch and corn starch packages will be provided for the study free of charge by Bob's Red Mill. Please see product specifications (**attached**)
- All starch for this study has been freely donated by Bob's Red Mill with no expectations or contracts. The starch has already been shipped to both sites.

• Nutritional label:

| DESCRIPTION   | VIDEOS | RECIPES | RELATED PRODUCTS | REVIEWS            | NUTRITIONAL INFO |
|---|--------|---------|------------------|--------------------|------------------|
| Nutrient Facts   |        |         |                  |                    |                  |
| Serving Size: 1 Tbs(12g)
Servings Per Container: 56  |        |         |                  |                    |                  |
|   |        |         |                  | Amount Per Serving | % Daily Value    |
| Calories  |        |         |                  | 40                 |                  |
| Calories from Fat   |        |         |                  | 0                  |                  |
| Total Fat   |        |         |                  | 0 g                | 0 %              |
| Saturated Fat   |        |         |                  | 0 g                | 0 %              |
| Trans Fat   |        |         |                  | 0 g                | 0 %              |
| Cholesterol   |        |         |                  | 0 mg               | 0 %              |
| Sodium  |        |         |                  | 0 mg               | 0 %              |
| Total Carbohydrate  |        |         |                  | 10 g               | 3 %              |
| Dietary Fiber   |        |         |                  | 0 g                | 0 %              |
| Sugars  |        |         |                  | 0 g                | N/A              |
| Protein   |        |         |                  | 0 g                | 0 %              |
| Vitamin A   |        |         |                  |                    | 0 %              |
| Vitamin C   |        |         |                  |                    | 0 %              |
| Calcium   |        |         |                  |                    | 0 %              |
| Iron  |        |         |                  |                    | 0 %              |
| * Percent Daily Values (DV) are based on a 2000 calorie diet. Your daily values may be higher or lower depending on your calorie needs. |        |         |                  |                    |                  |
| Ingredients:  |        |         |                  |                    |                  |
| potato starch   |        |         |                  |                    |                  |
| *Manufactured in a facility that also uses tree nuts and soy  |        |         |                  |                    |                  |

**Packaging and Delivery of potato starch (active) and corn starch (placebo) (600 grams and 500 grams respectively):**

As this is a double blinded randomized control trial, investigators and participants will not be made aware of participant allocation to intervention or placebo starch.

To ensure blinded study design, as well as safe packaging and shipment of starch the following steps will take place:

- Starch was delivered from Bob's Red Mill free of charge to:  
Yale Investigational Pharmacy ([name])
- Similarly, starch was delivered from Bob's Red Mill free of charge to Michigan site.
- Only the pharmacist will hold the labeling key and will repackage the starch. The manufacturer packaging will be removed and the starch will be emptied into a pre-labeled freezer ziploc bag. To ensure secure packaging of starch, each amount (either 600 or 500 grams depending on type of starch) will be double bagged for safety. Labeling will comply with labeling regulations.
- Starch packages will be repackaged and labeled at Yale's investigational drug services (IDS) who will be responsible for dispensing the starch, keeping drug accountability logs and compliance with any relevant state requirements. Research study team will package the starch at University of Michigan and the IDS at Michigan will dispense and ship the starch accordingly.
- A generated list of enrolled participants randomized to intervention or placebo by stratified permuted block randomization will be given to IDS who will ship starch based on patient allocation.

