**Figure 7. Trial Design**

**attached instructions**) on how to take the RPS or placebo for the duration of the trial. Patients will be asked to take 2 tablespoons (~20 grams) of RPS in water or juice or applesauce (any cool substance to make it palatable) twice daily for 14 days with the same instructions for the placebo arm. Patients will be called every 2 days while taking RPS to assess symptoms and adverse events via a pre-specified questionnaire (**see attached questionnaire**) for the first 14 days and then will be called weekly until 30 days after the last dose of treatment. Patients are then followed via EHR to complete the 4-months follow up from the time of diagnosis (ie. COVID test positive) (**Figure 7**). Of note, the placebo will be identical in appearance and packaging as the RPS. Both food ingredients, placebo and RPS, are isocaloric (approximately 140 calories per day from either food ingredient). The placebo has been safely used as a control in human clinical trials (NCT 02763033, NCT01939600, NCT01708694).

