## Treatment Dosage and Administration

RPS or placebo will be administered at ~20 grams (2 tablespoons) once daily for days 1-3 and then twice daily for days 4-14, (**Table 2**).

Intervention and Placebo:

**Table 2.** Intervention and Placebo

|              |                                    |   |
|--------------|------------------------------------|---|
| Intervention | Study Product, Dose, Route Regimen | Food Source (used as a drug): Potato based dietary starch, Bob's Red Mill®, ~20 grams (2 tablespoons) orally twice daily. (start with 2 tablespoons once daily for 3 days, followed by twice daily on days 4 to 14 to minimize GI symptoms) |
|              | Duration of Administration         | 14 days   |
| Placebo      | Study Product, Dose, Route Regimen | Food Source (used as a drug): Corn based dietary starch by Bob's Red Mill, ~20 grams (2 tablespoons) orally twice daily. (start with 2 tablespoons once daily for 3 days, followed by twice daily on days 4 to 14)                          |
|              | Duration of Administration         | 14 days   |

- Storage and stability: Avoid extremes of temperature. No need for refrigeration.
- Preparation and Dispensing: Mix 2 tablespoons of dietary starch (~20 grams) with any amount water, juice, applesauce or any other cool substance to make palatable. Starch substance should not be heated or warmed.
- Other administration instructions: No regulation for administration of starch with or without other food or medications. As this is a commercially available food product, subjects can keep any remaining product at the end of study. We will determine compliance via questionnaire that will be utilized during phone follow ups (**see attached questionnaire**). Doses should be administered twice daily. Although we suggest the doses be spread apart to minimize any potential GI disturbance, there is no limit as to how closely together doses can be given. For example, doses do NOT need to be given 12 hours apart and instead can be given at times that feel comfortable to the subject.
- Missed doses should be documented by the research team during phone follow up
- Missed doses should simply be skipped with no need to make up this dose at a later time.
- Availability: Commercially Available

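### Bags are filled by product (600 g active, 500 g placebo) and the protocol prints which is which: an avoidable route to unblinding, though not evidence that anyone was unblinded

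*Combined protocol and SAP*

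**What the plan says.** Three parts of Section 4 bear on this.

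- **Fill.** The section headed "Packaging and Delivery of potato starch (active) and corn starch (placebo) (600 grams and 500 grams respectively" gives the weight for each arm, and its packing step repeats that the weight depends on the type of starch: "each amount (either 600 or 500 grams depending on type of starch) will be double bagged for safety". Both statements belong to a list of steps introduced as protecting the blinded design.
- **Blind.** The Study Design text says "the placebo will be identical in appearance and packaging as the RPS". The Blinding section says "The study will be double blinded to patients and investigators".
- **Who packs.** The packaging section says "Only the pharmacist will hold the labeling key and will repackage the starch", and then says "Research study team will package the starch at University of Michigan", with the investigational drug service there dispensing and shipping. The Blinding section likewise names pharmacists as packers, but ends by sending the randomization lists to research staff who package.

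No section equalises the two weights, explains the difference, or keeps the weights from blinded staff. Appendix B tells every participant that the bag should be used up by day 14. Drug Information lets participants keep whatever remains.

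**The concern.** A placebo that differs from the active product in one fixed, measurable property is not fully matched. Here the property is net weight, and the rule that decodes it is printed in the protocol that the blinded team works from. Someone who lifts or weighs a sealed bag, or reads a shipping weight, and who knows the rule can infer the arm without the labeling key.

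The blind protects two kinds of judgement. Recovery time and symptom score are self-reported to a caller. Whether an admission counts as COVID-19 related, which decides the primary outcome, is adjudicated by the site PI. If allocation became known to those who make or record these judgements, both could be biased.

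Leftover product is a second possible cue. If one arm tends to finish the bag and the other does not, the Appendix B instruction gives a participant a reason to mention it. The Appendix A call asks whether starch was taken as instructed, and the same call scores symptoms.

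**Working it through.** **Weight difference.** 600 − 500 = 100 g, and 100 / 500 = 20%. The active bag holds 20% more than the placebo bag. Double bagging adds the same tare to both, so the 100 g gap remains in the sealed bag.

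**Tablespoons scheduled.** Treatment Dosage and Administration says "RPS or placebo will be administered at ~20 grams (2 tablespoons) once daily for days 1-3 and then twice daily for days 4-14". Doses = 3 × 1 + 11 × 2 = 25, and 25 × 2 = 50 tablespoons in each arm.

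**Do the two fills follow from the plan's own figures?** No derivation is given, so I tried each basis the documents offer. Need = 50 × grams per tablespoon.

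- The regimen equates 2 tablespoons with about 20 g, so 10 g per tablespoon, for both products.
- The potato label reads "Serving Size: 1 Tbs(12g" grams), so 12 g per tablespoon.
- Section 1 gives corn starch calories per 8 g. That 8 g is one tablespoon is an assumption; no passage says so.

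| Grams per tablespoon | Potato need | Left from 600 g | Corn need | Left from 500 g |
|---|---|---|---|---|
| 10 both | 500 g | 100 g | 500 g | 0 |
| 12 potato, 8 corn (assumed) | 600 g | 0 | 400 g | 100 g (12.5 tablespoons) |
| 12 potato, 10 corn | 600 g | 0 | 500 g | 0 |

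The third row reproduces both fills exactly and leaves nothing over in either arm. It takes the potato figure from the label and the corn figure from the regimen, although the regimen states the same 10 g per tablespoon for potato. It is a possible reason for the two weights, but not a stated one.

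Equal calories is another candidate. At 140 kcal per day for 14 days (140 × 14 = 1960 kcal), the Section 1 values give 1960 / (40/12) = 588 g potato and 1960 / (30/8) = 523 g corn. The specifications in Appendices C and D give 1960 / 3.27 = 599 g and 1960 / 3.62 = 541 g. Neither pair is 600 and 500.

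The Study Design text describes twice-daily dosing for all 14 days. That is 28 doses, or 28 × 20 = 560 g, which matches neither bag.

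**Would simply equalising the weights work?** On 12 and 8 g per tablespoon, a common weight W holds W/12 potato tablespoons and W/8 corn tablespoons, a gap of W/24.

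- Present fills: 600/12 = 50 and 500/8 = 62.5, gap 12.5.
- Both at 600 g: 50 and 75, gap 25.
- Both at 500 g: 41.7 and 62.5, gap 20.8, and the potato bag falls short of the 50 scheduled.

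On 12 and 10 g per tablespoon, both at 600 g gives 50 and 60, where the present gap is zero. Equal weight on its own therefore removes the weight cue and enlarges the leftover cue.

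**The case against.** The strongest reply is that few people could use this cue.

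- The pharmacist holds the key, and the drug service ships from the allocation list, so weight tells them nothing new. Whoever empties the manufacturer's packs sees the product anyway.
- Each participant receives one bag at home, with nothing to compare it against. Appendix B states no weight.
- Appendix A asks about adherence and side effects, not about weight or leftovers. Remaining product is kept, not returned. A caller would need an unprompted remark and would have to recall the 600/500 rule.
- Nothing has the adjudicating site PI handling bags.
- Identical packaging can fairly be read as the same double freezer bag. If the third row of the table is the reason for the fills, the two bags also hold equal numbers of tablespoons.

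Most of this stands. A reader might infer that participants, callers or adjudicators can identify the arm, or that the blind is broken. The documents do not support that. What remains is narrower. At Michigan the packers belong to the research team, and nothing says which of their colleagues later handle or log the sealed bags. The decoding rule sits in a document that they use. Even a sound volume or calorie reason for the fills would leave the 100 g difference in place.

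**Conclusion.** The point holds in a limited form. The fills contradict the claim of identical packaging if that claim covers net weight. The 100 g (20%) difference is a complete marker of arm for anyone who both meets a sealed bag or its shipping weight and knows the rule. The most plausible exposure is among study staff at Michigan; callers are a less likely one.

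This rests on two assumptions: that blinded staff can read the protocol, and that some of them see sealed bags or shipping weights. The documents neither confirm nor exclude the second. The direction and size of any leftover depend on grams per tablespoon, which the documents do not settle: from none in either arm to 100 g in one of them.

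No bias in the primary or secondary outcomes can be quantified from this. It deserves correction because it is avoidable at small cost, not because harm has been shown.

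**What to change.** 1. Move product-specific fill weights out of the protocol, labels, shipping records and anything else that blinded staff can see, into an unblinded pharmacy manual.
2. Fill both products so that neither sealed weight nor expected leftover identifies the arm. One option is a common net weight that covers the schedule for both products with some excess in each. Unblinded pharmacy staff should first weigh actual tablespoons of each product, because equal weight alone can widen the leftover gap.
3. Delete or revise the Appendix B sentence about finishing the bag, so that leftover starch is unremarkable in either arm. This also removes the tension with letting participants keep the remainder.
4. Reconcile Study Design, Blinding, Drug Information, the packaging section, Treatment Dosage and Administration, and Appendix B on grams per tablespoon, schedule, fill and who packs. The common weight can be set only after that. No dose is proposed here.

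The cost is up to about 100 g, or somewhat more, of donated starch per bag, a revised packing instruction and a document revision. Participants will have some product left, and bag volume may differ slightly between products. If grams per tablespoon differ, a common weight still leaves unequal remainders, so step 3 is needed alongside step 2.

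### The protocol contradicts itself on who repackages the starch and who receives the randomization lists, so the blind at Michigan is not assured

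*Combined protocol and SAP*

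**What the plan says.** The section on packaging and delivery of the two starches sets out steps meant to protect the blind. Its general rule is "Only the pharmacist will hold the labeling key and will repackage the starch". It describes the task this way: "The manufacturer packaging will be removed and the starch will be emptied into a pre-labeled freezer ziploc bag". At Yale, repackaging and labeling are given to IDS. For Michigan the arrangement differs: "Research study team will package the starch at University of Michigan and the IDS at Michigan will dispense and ship the starch accordingly". The same section promises that "investigators and participants will not be made aware of participant allocation to intervention or placebo starch", and says that the list of randomized participants "will be given to IDS who will ship starch based on patient allocation".

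The Blinding section says "The study team will include investigational pharmacists who will package the intervention RPS and placebo starch", and that these pharmacists "will not share the labeling key code with any of the other study members who are performing the study". Its closing sentence says that the team "will generate randomization lists to be sent to the research staff members who will package the starch to deliver the designated packages to participants". The Randomization section, by contrast, sends the lists to the investigational pharmacy.

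**The concern.** A blind of this kind depends on a clear division between the people who handle identified product or allocation lists and the people who consent, call, record and adjudicate. Here the division is stated one way as a general rule and another way for one of the two named sites. A site following the Michigan sentence would have study staff handling product whose identity they know. If it also followed the list sentence in Blinding, the same staff would hold the allocation list.

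Two kinds of outcome depend on the blind. Under Primary Outcome Measure, the site PI decides whether each admission counts as COVID-19 related. The two secondary outcomes, time to clinical recovery and the symptom severity score, are patient reports taken down by phone. If knowledge of the arm reached a caller or adjudicator, events or symptoms could be recorded differently by arm, and no later analysis could restore the blind.

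**Working it through.** No arithmetic applies: the plan states no figure on this point. The check is a comparison of the sections.

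**1. Who packages, and who gets the list**

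| Place in the protocol | Who packages | Who receives the list |
|---|---|---|
| Packaging section, general rule | Pharmacist only | IDS |
| Packaging section, Yale | IDS | IDS |
| Packaging section, Michigan | Research study team (IDS dispenses and ships) | IDS |
| Blinding, pharmacist sentence | Investigational pharmacists | Not stated |
| Blinding, list sentence | Research staff members | Research staff members |
| Randomization | Investigational pharmacy | Investigational pharmacy |

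The first and third rows cannot both be true at Michigan. Unless the staff in the fifth row are pharmacists, that row conflicts with the first and last on packaging and on the list.

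**2. What a non-pharmacist packager at Michigan would know.** The packager would handle identified product: potato starch at 600 g or corn starch at 500 g. If Michigan uses the bags labeled in advance that the general rule describes, the packager would also see label and contents together, and would not need the key to link them. That "if" is needed, because the labeled-bag step sits in the pharmacist rule. The Michigan sentence mentions only packaging and does not say who labels or when.

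**3. What it takes to learn a participant's arm.** Knowing which label holds which starch is not enough. The packager must also learn which label went to which participant, or see the list. The packaging section gives the participant list to IDS, which closes that route. The list sentence in Blinding, read literally, opens it again.

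**4. Whether the stated safeguards cover these packagers**

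- Non-disclosure of the key code (Blinding): binds the investigational pharmacists and names nobody else.
- Key held only by the pharmacist (packaging section): does not cover someone who sees contents and label together.
- Participant list to IDS (packaging section): helps, but the list sentence in Blinding conflicts with it.
- Investigators not told the allocation (packaging section): states the aim, without a control on non-pharmacist packagers.

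**5. Whether a separation is stated elsewhere.** None was found. The protocol uses its team terms broadly. The PI or Co-I who confirms eligibility belongs to the study team (Subject Screening, Enrolment, and Recruitment). A study team member explains the study for consent (Subject information and Consent). The research team records missed doses on the calls (Drug Information). All study team members join the two-weekly conferences on reported events (Multicenter Coordinating Plan). This does not show that the same people do these tasks. It shows only that the wording does not keep the packagers out of them.

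**The case against.** The best defence is that the research study team at Michigan simply means pharmacists, since Blinding counts investigational pharmacists within the study team. That may well explain the research staff members in the list sentence of Blinding. It is weak for the Michigan sentence, which names the Michigan IDS separately, gives it a different task, and follows directly on a Yale sentence that gives repackaging to IDS.

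A second defence is that the plan has more than one safeguard. This stands. A reader might infer that the pharmacists' non-disclosure rule is the only barrier, and that would be wrong: the packaging section also restricts the key, directs the participant list to IDS and says investigators will not learn the allocation. These safeguards make leakage less likely, but they do not say how non-pharmacist packagers are kept apart from blinded work.

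Third, the conference calls do not single out the Michigan packagers. Read literally, they would include the pharmacists who hold the key as well. That is fair, and the calls are only weak evidence of exposure.

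Fourth, the secondary outcomes are reported by participants who are themselves blinded, on a scripted questionnaire with four levels per symptom. A caller who knew the arm could still affect what is recorded, but the scope is limited.

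A reader might also infer that the primary test's false-positive rate is inflated by a calculable amount. The documents do not support this. Such a figure would need the chance that an adjudicator knows the arm and the rate at which that adjudicator would misclassify admissions. The plan gives neither, and it says investigators are blinded. Any result would measure the assumptions chosen.

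**Conclusion.** The contradiction is established by the text: the packaging section gives two incompatible answers on who packages at Michigan, and the list sentence in Blinding does not fit the Randomization and packaging sections unless its research staff are pharmacists. It follows that the blind at Michigan is not assured. A reader might go further and conclude that it is broken. The documents do not show that: nothing says callers or adjudicators will know any participant's arm.

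No numerical effect is claimed. How much of the trial is exposed depends on Michigan's share of enrollment, which Section 14 leaves open by letting sites accrue unequally toward 1500. The conclusion rests on two readings: that the Michigan team is distinct from the Michigan IDS, as the sentence itself suggests, and that no separation rule exists in material not included here. It should be fixed, because it concerns the handling of product and lists in a trial whose primary outcome is adjudicated at the site.

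**What to change.** Reconcile the Randomization, Blinding and packaging sections so that, at both sites, only the IDS or investigational pharmacy receives the list, holds the key, repackages and labels. Michigan's IDS would continue to dispense and ship.

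If Michigan study staff must package, then:

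- designate existing named roles as unblinded packagers;
- withhold the participant list from them;
- extend the non-disclosure rule in Blinding to them;
- bar them from participant contact, outcome data collection, adjudication, and the part of the two-weekly calls where participants' events are discussed.

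The cost is wording in three sections plus some Michigan pharmacy time or reassignment of existing staff. The documents do not give pharmacy capacity. As a rough scale, if Yale met its target of 500 and Michigan were the only other site, 1500 − 500 = 1000 participants' packages would be prepared at Michigan. Sample size, visit schedule and outcomes do not change.
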